#### 10.5 Unanticipated Adverse Device-related Event Definition

An unanticipated adverse device-related event is any serious adverse effect on health or safety, any life-threatening problem or death caused by, or associated with a device, if that effect, problem, or death was not previously identified in nature, severity, or degree of incidence in section Known Potential Risks.

# 10.6 Adverse Event Reporting

When an adverse event occurs, the following information and assessments in the adverse event section of the CRF will be recorded:

- The signs, symptoms or diagnosis of the event
- The date and time of onset and termination of the event (24-hours clock format where midnight is 00:00 and noon is 12:00)
- The adverse event severity using the criteria outlined above
- The relationship of the event to the investigational device as outlined above
- A description of any action taken regarding study device disposition
- A list of any required therapy, medication, treatment or diagnostic procedure
- Clinical behavior prior to the event, such as nutrition, medicine, physical activity etc.
- Any additional data which might be relevant to the event

The investigator is responsible for the appropriate medical management of all adverse events and for the personal safety and well-being of the subjects.

# 10.7 Serious Adverse Events Reporting and Unanticipated Adverse Device-Related Events (UADE)

Any serious and/or unexpected and/or device related adverse event must be reported to the sponsor- CorNeat Vision and the Clinical Study Monitor via the EDC system. Full details of the event, treatment, and an assessment of the relationship between the investigational device must be provided in the report. The report shall be prepared by the principal investigator. Reports relating to the subject's subsequent medical course must be submitted to the sponsor until the event has subsided or, in case of permanent impairment, until the event stabilizes, and the overall clinical outcome has been ascertained.

CorNeat Vision will notify all investigators in writing of severe/serious or unexpected adverse events when this information is of global importance to subject safety and welfare. Reporting to the EC/REB will be done according to local regulation.

### 10.8 Known Potential Risks

Known risks from usage of similar artificial corneas are:

- Postoperative Corneal Melt is one of the most severe complications that can occur after keratoprosthesis surgery with incidence of up to 30%. It may lead to scarring, irregular astigmatism, photophobia, decreased vision, and even endophthalmitis.
- Lack of graft retention Corneal grafts tissue artificial integration is limited and with time the bond between the implant and eye weakens. E.g. Boston KPro's retention rates decreases over time with incidence of lack of retention of 6, 11 and 25% after 1, 2- and 5-years post-op, respectively.
- Post-operative Glaucoma is the most important threat to long-term preservation of vision following Boston KPro surgery with elevation of intraocular pressure in 19–38 % of patients postoperatively and progression of pre-operative glaucoma in 7–14 % of patients. Development of glaucoma de novo following Kpro placement has been reported in 2-28% of KPro recipients .
- Poor post-operative visual quality Eyes with current KPros have very limited visual field and poor visual function. About 50% of patients implanted with Boston KPro maintain 20/200 CDVA after 8 years from surgery .

<sup>6 Bouhout, S., Robert, M.C., Deli, S. and Harissi-Dagher, M., 2018. Corneal melt after Boston keratoprosthesis: Clinical presentation, management, outcomes and risk factor analysis. Ocular immunology and inflammation, 26(5), pp.693-699.

<sup>7 Schaub, F., Bachmann, B.O., Seyeddain, O., Moussa, S., Reitsamer, H.A. and Cursiefen, C., 2017. Mid-and longterm experiences with the Boston-keratoprosthesis. The Cologne and Salzburg Perspective. Klinische Monatsblatter fur Augenheilkunde, 234(6), p.770.

<sup>8 Jin, B. and Zhu, X., 2017. The pathogenesis and prevention of corneal graft melting after keratoplasty. J Clin Ophthalmol, 1(1), p.10.

<sup>9 Ciolino, J.B., Belin, M.W., Todani, A., Al-Arfaj, K., Rudnisky, C.J. and Boston Keratoprosthesis Type 1 Study Group, 2013. Retention of the Boston keratoprosthesis type 1: multicenter study results. Ophthalmology, 120(6), pp.1195-1200.

- Retro-KPro membranes (RPM) formation- are the most common complication in KPro implanted patients, with an incidence of 27-47.6%.

RPM is usually treated with Nd:YAG membranotomy which can cause retinal detachment in 26.7%.

• Endophthalmitis - The incidence of endophthalmitis in KPro patients is relatively high (1.2-11.4%) even in patients with prophylactic antibiotic topical treatment.

Other risks include:

- Transient inflammatory reaction around the eye
- Vitreous hemorrhage- bleeding inside the eye
- Vitritis- sterile inflammation inside the eye
- Retinal Detachment- separation of the retina from the wall of the eye resulting in loss of vision
- Ptosis- a droopy eyelid
- Foreign body sensation

# **10.9** Device Explantation

# **10.9.1 Potential Clinical Scenarios Resulting in Device Explantation**

Potential clinical scenarios resulting in the removal of the CorNeat KPro can be attributed to the following three pathological processes:

- Severe retroprosthetic membrane (RPM) formation Most RPMs are typically treated with neodymium:yttrium-aluminum-garnet (Nd:YAG) laser membranotomy or by surgical membranectomy. However, when an aperture cannot be created in the membrane with either method, the keratoprosthesis should be replaced.
- Infection may occur due to bacterial, viral, fungal or parasitic pathogens that entered the eye. This will be prevented using prophylactic use of antibiotics and intra-surgical antiseptic technique. In the case of an active infection in the eye, the ophthalmologist will opt for urgent intervention to retrieve a specimen for cultures and to inject potent

 <sup>18 Sayegh, R.R., Diaz, L.A., Vargas-Martín, F., Webb, R.H., Dohlman, C.H. and Peli, E., 2010. Optical functional properties of the Boston keratoprosthesis. Investigative ophthalmology & visual science, 51(2), pp.857-863.
  Chen, W., 2015. Innovative Method to Avoid the Open-Sky Condition in Penetrating Keratoplasty and the Triple

<sup>19 Chen, W., 2015. Innovative Method to Avoid the Open-Sky Condition in Penetrating Keratoplasty and the Triple Procedure: Securing the Anterior Chamber. Cornea, 34, p.S113.
 Carting, M.S. and de la Cruz, L. 2015. Keratoprosthases and Artificial Corneas. Fundamentals and Surgical

<sup>20 Cortina, M.S. and de la Cruz, J., 2015. Keratoprostheses and Artificial Corneas. Fundamentals and Surgical Applications, p.2015.

**CONFIDENTIAL** - THIS DOCUMENT CONTAINS CONFIDENTIAL AND PROPRIETARY INFORMATION. THIS DOCUMENT MAY NOT BE REPRODUCED, USED, OR DISCLOSED TO ANY THIRD PARTY WITHOUT PRIOR WRITTEN CONSENT.

antibiotics intravitreally. Endophthalmitis patients may also require an urgent surgery (pars plana vitrectomy), and evisceration may be necessary to remove a severe and intractable infection which could result in a blind and painful eye.

• Tissue necrosis - can result in corneal perforation, hypotony, and / or instability, leading to extrusion of the device. Based on the severity and specific circumstances of each case, the surgeon may decide either to replace the CorNeat KPro with another artificial cornea, seal the eye with a donor cornea or perform an evisceration or enucleation procedures.

# **10.9.2 Device Explantation Procedure**

Upon reaching the decision to remove the device, the surgeon may choose one of the following surgical approaches according to the specific ocular condition and per his/her discretion:

- 1) Releasing the skirt component from under the overlying conjunctiva using sharp dissection.
- Removal of only the optic component of the CorNeat KPro while the skirt component remains under the overlying conjunctiva. This will be performed by cutting the skirt around the optic componenet with an appropriate blade or scissors throughout the entire circumference.

The eye will be implanted with either a replacement CorNeat KPro, tectonic corneal graft or an alternative artificial cornea.

It should be noted that in severe cases of the above-mentioned complications, evisceration or enucleation might be the only options remaining.

# 10.10 DSMB

The ten first implanted subjects will comprise the first-in-human cohort. Once the 10th subject successfully completes the 6th month post-surgery follow-up, an independent data-safety-monitoring-board (DSMB) will review the data and submit its conclusions to the study sponsor. Copies will be forwarded to the REB and to the Ministry of Health.

In order to manage the FIH cohort for DSMB submission participating sites will inform sponsor upon subject screening via subject screening log.

# 10.11 Premature Termination or Suspension of the Study

The trial will be stopped if severe side effects or infections, resulting in device removal and related with the investigational device, are diagnosed in three patients.

In case of premature termination of the study, the PIs will decide regarding the required future follow up for each patient on a case by case basis.

The trial may be temporarily suspended if there is sufficient reasonable cause.

Circumstances that may warrant termination or suspension include, but are not limited to:

• Determination of unexpected, significant, or unacceptable risk to participants

**CONFIDENTIAL** - THIS DOCUMENT CONTAINS CONFIDENTIAL AND PROPRIETARY INFORMATION. THIS DOCUMENT MAY NOT BE REPRODUCED, USED, OR DISCLOSED TO ANY THIRD PARTY WITHOUT PRIOR WRITTEN CONSENT.

- Demonstration of poor efficacy that would warrant stopping
- Insufficient compliance to protocol requirements
- Data that are not sufficiently complete and/or evaluable

If the study is suspended, the PIs will promptly inform the EC and will provide the reason(s) for the suspension. Study may resume once concerns about safety, protocol compliance, and data quality are addressed and satisfy the sponsor, EC, and /or respective regulatory agency.

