#### UNCONTROLLED WHEN PRINTED

subjects will be enrolled in the study. Demographic data, medical history and concomitant medication use data will be collected from enrolled subjects. Subjects will be implanted with the CorNeat KPro, and followed-up over a period of 12 months in 8 clinic visits. During follow up visits safety data and use of concomitant medication will be documented. Subjects accrual is planned for a maximum of 12 months and overall first subject in to last subject out is planned for 24 months.

Follow up plan will include complete clinical exam, anterior segment photography and a questionnaire assessing pain and other possible subjective ramifications.

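### The only DSMB review written in the protocol comes after all ten implants, and no serious eye event managed with the device in place is sent to the DSMB sooner

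*Protocol*

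**What the plan says.** **Mandatory stop.** Protocol section 10.11 has one rule under which the trial must stop: "if severe side effects or infections, resulting in device removal and related with the investigational device, are diagnosed in three patients".

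**Discretionary stop.** The rest of 10.11 is permissive. A list introduced by "Circumstances that may warrant termination or suspension include, but are not limited to" includes unacceptable risk to participants. It gives no count and names no event. After a suspension, the study may resume once the concerns are "addressed and satisfy the sponsor, EC, and /or respective regulatory agency".

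**DSMB.** Under 10.10, once the tenth subject has completed the month-6 visit, "an independent data-safety-monitoring-board (DSMB) will review the data and submit its conclusions to the study sponsor", with copies to the REB and the Ministry of Health. The Synopsis (Safety Assessment) gives the same timing. No other DSMB review appears in the protocol.

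**Timetable.** The Synopsis (Conduct of clinical study) says: "Subjects accrual is planned for a maximum of 12 months".

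**Event reporting.** Section 10.7 says: "Any serious and/or unexpected and/or device related adverse event must be reported to the sponsor". The route is the EDC system, and the study monitor also receives the report. For the ethics side, "Reporting to the EC/REB will be done according to local regulation". The DSMB is not named as a recipient. The Synopsis (Safety management) gives oversight to the sponsor's medical monitor.

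**The concern.** In a first-in-human implant study with ten sequential patients, independent review does most for patients between implants, when it can still change whether the next eye is operated on. Here the DSMB's only written review comes when no cohort implant remains.

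The mandatory stop fills that gap only for harms that end in device removal. Section 10.9.1 attributes removal to three processes: severe retroprosthetic membrane, infection and tissue necrosis. Section 10.8 also lists retinal detachment and suprachoroidal haemorrhage, which are not among those causes. Endophthalmitis is first managed with cultures, intravitreal antibiotics and sometimes vitrectomy (10.9.1), so some of these eyes keep the device. A patient could suffer a serious eye harm, keep the implant and add nothing to the count of three. Whether implantation continues would then be decided without any written requirement for an independent view.

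**Working it through.** The protocol gives no operating figure for the stopping rule or the DSMB review, so there is none to reproduce. The point rests on wording and timing; the arithmetic only illustrates its size.

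**1. Timing of the review.** Maximum planned accrual of 12 months, plus the tenth subject's month-6 visit: 12 + 6 = about 18 months after the first implant (visit window ±14 days). Implants still to come in the cohort: 10 − 10 = 0.

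**2. Who sees a serious eye event with the device retained.**
- Sponsor and study monitor: yes, through the EDC (10.7).
- EC/REB: yes, as local regulation requires (10.7).
- Mandatory count of three: no, unless the device is removed (10.11).
- DSMB: only at the single scheduled review (10.10).
- UADE status (10.5): this needs a serious effect "not previously identified in nature, severity, or degree of incidence in section Known Potential Risks". A single listed harm of known severity would not readily qualify, and 10.8 gives no numerical incidence for suprachoroidal haemorrhage that could be exceeded. In any case, a UADE follows the 10.7 route and does not go to the DSMB.

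**3. Illustrative number of events before the tenth implant.**

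Inputs from 10.8, for similar devices:
- Retroprosthetic membrane: 27% to 47.6%.
- Retinal detachment after laser membranotomy: 26.7%.
- Endophthalmitis: 1.2% to 11.4%.

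Assumptions, none of them given in the protocol: these rates apply over 12 months (10.8 states no time horizon for them), accrual is even over 12 months, the hazard is constant and events do not overlap.

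Per-subject 12-month probability, p = membrane rate × share lasered × 0.267 + endophthalmitis rate:
- All membranes lasered, low: 0.27 × 0.267 + 0.012 = 0.0841.
- All membranes lasered, high: 0.476 × 0.267 + 0.114 = 0.2411.
- Half lasered, low: 0.5 × 0.27 × 0.267 + 0.012 = 0.0480.
- Half lasered, high: 0.5 × 0.476 × 0.267 + 0.114 = 0.1775.

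Follow-up before the tenth implant: ten implants evenly spaced over 12 months are 12/9 months apart. The time accrued before the last is (12/9) × (9 + 8 + … + 1 + 0) = (12/9) × 45 = 60 person-months. Total follow-up is 10 × 12 = 120 person-months, so half of it, equal to 5 subject-years, falls before the tenth implant.

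Expected events are about 5p, and P(at least one) = 1 − (1 − p)^5:

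| Scenario | p | Expected events | P(at least one) |
|---|---|---|---|
| All lasered, low | 0.0841 | 0.42 | 36% |
| All lasered, high | 0.2411 | 1.21 | 75% |
| Half lasered, low | 0.0480 | 0.24 | 22% |
| Half lasered, high | 0.1775 | 0.89 | 62% |

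These are events that would be referred to the DSMB, not probabilities of vision loss. Suprachoroidal haemorrhage is left out because 10.8 gives no rate for it.

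**The case against.** **The trial is not unmonitored.** A reader might infer that nobody can act on such harms until month 18 or until three devices are removed. The documents do not support that. Serious and device-related events are reported as they occur. The sponsor informs all investigators in writing of those important to safety (10.7). A medical monitor oversees safety, and the study monitor takes part in the initial implantations and follow-up visits (12.3). The EC/REB receives status reports at least yearly (12.10). Section 10.11 allows suspension or termination for unacceptable risk at any time, on grounds that are expressly not exhaustive. All of this stands. What these measures lack is a required independent look before the next implant.

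**The mandatory rule is not shown to be wrong.** A reader might infer that a second binding stop, based on vision, is needed. With ten subjects, keeping one hard rule and leaving other harms to judgement is defensible, and the protocol does not contradict itself here. Listed complications are likely enough at the 10.8 rates that a hard stop could be triggered by a device that merely matches them.

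**The size is uncertain.** Counting all events over 12 months in all ten subjects would double the expected numbers, but events after the tenth implant cannot bear on whether implants continue. Even the halved figures may be too high. The source rates have no time horizon, surgical membranectomy is an alternative to laser (10.9.1), faster accrual leaves less follow-up before the last implant, and some infections would end in removal and already count.

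**A charter may cover it.** Event-triggered reviews may sit in a DSMB charter that is not shown. If so, the point falls away except for a cross-reference.

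**Conclusion.** The point holds in a limited form. As the protocol is written, the DSMB's only review cannot affect any of the ten cohort implants, and the only mandatory stop does not count serious eye harms managed with the device in place. Those harms reach the sponsor, its monitors and the EC/REB, and any suspension is discretionary. The gap is therefore in early independent review; oversight as a whole is not absent.

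Under the stated assumptions, between roughly one in five and three in four such trials would see at least one detachment or endophthalmitis event before the tenth implant (22% to 75% across the two laser scenarios). The share of these with the device retained is unknown. The conclusion does not depend on these figures, since it follows from 10.7, 10.10 and 10.11 read together. It is confined to this protocol because a DSMB charter could add triggers.

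**What to change.** Keep the removal rule and add to 10.10 and 10.11:

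> Any device- or procedure-related (including treatment of a device complication) endophthalmitis, retinal detachment, suprachoroidal haemorrhage, loss of light perception, or serious loss of vision from baseline in the study eye is sent to the DSMB when reported in the EDC, whether or not the device is removed. The DSMB recommends in writing, before the next implant, whether implants continue, pause or stop.

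This adds early independent review; it does not add a second mandatory stop. If a charter already provides for it, a cross-reference in 10.10 is enough.

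The cost is an amendment of a few sentences that uses the existing DSMB and EDC, a few ad hoc DSMB reviews, and possibly a short wait before the next implant.

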# 7 Study Population and Subject Selection

# 7.1 Study Population

10 subjects suffering from unilateral or bi-lateral corneal blindness not reasonably amenable by transplanting human tissue. The KPro can be implanted in OD or OS (selection is according to PI discretion).

UNCONTROLLED WHEN PRINTED

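### Section 10.11's only mandatory numeric stop needs three qualifying device removals whatever the number implanted; at a 24% removal rate it is never met in about 56% of trials and seldom acts before the last implant

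*Protocol*

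**What the plan says.** - **Mandatory stop (Protocol 10.11).** The trial stops when "severe side effects or infections, resulting in device removal and related with the investigational device, are diagnosed in three patients". The rule gives no denominator and no schedule for looking.
- **Discretionary suspension (10.11).** "The trial may be temporarily suspended if there is sufficient reasonable cause". The listed circumstances, which include unacceptable risk to participants, carry no number and oblige no one to act.
- **Scheduled review (10.10).** One DSMB review is described, once the tenth subject has completed the month 6 visit. By then all ten implants have been done.
- **Size and pace.** Section 7.1 plans "10 subjects suffering from unilateral or bi-lateral corneal blindness not reasonably amenable by transplanting human tissue". In the Synopsis (Conduct of clinical study), "Subjects accrual is planned for a maximum of 12 months". Each subject is followed for 12 months. No minimum interval between implants is described.
- **Benchmark (10.8).** For the Boston KPro the protocol cites "incidence of lack of retention of 6, 11 and 25% after 1, 2- and 5-years post-op, respectively".
- **What removal covers (10.9).** Section 10.9.1 lists tissue necrosis with extrusion among the scenarios that end in removal. Section 10.9.2 begins "Upon reaching the decision to remove the device, the surgeon may choose one of the following surgical approaches", and one of these approaches takes out the optic alone and leaves the skirt in place.

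**The concern.** In a first-in-human device study, a stopping rule mainly protects subjects who have not yet been implanted. A fixed count of three in a cohort of ten can fail them in two ways. It may not be reached even when the device loses far more eyes than existing devices do. It may also be reached only after everyone has been implanted, because removals accrue over 12 months per subject while accrual itself takes at most 12 months. No scheduled review falls inside the implantation period to cover either gap.

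There is a second, smaller point. With a trigger of three, whether one borderline loss counts can decide the outcome, and 10.11 does not say what counts as removal. If sites count an extrusion or an optic-only removal differently, the rule changes with them.

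**Working it through.** The protocol gives no operating characteristics for this rule, so there is no figure of its own to reproduce.

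**Inputs.** n = 10 (7.1); trigger of 3 patients (10.11); 12 months of follow-up per subject and accrual of up to 12 months (Synopsis; section 6); reference one-year loss of 6% (10.8). The scenario of four times the reference is 4 × 6% = 24%. It is an assumption of this check, not a figure in the protocol.

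**Step 1: is the rule ever met?** With p the 12-month probability of a qualifying removal and X ~ Binomial(10, p), the rule is missed when X ≤ 2. At p = 0.24:

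- P(X = 0) = 0.76^10 = 0.064
- P(X = 1) = 10 × 0.24 × 0.76^9 = 0.203
- P(X = 2) = 45 × 0.24² × 0.76^8 = 0.288
- P(missed) = 0.556, so P(met) = 0.444

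| True 12-month rate | P(at least 3 of 10) | P(at least 2 of 10) |
|---|---|---|
| 6% | 0.019 | 0.118 |
| 12% | 0.109 | 0.342 |
| 18% | 0.263 | 0.561 |
| 24% | 0.444 | 0.733 |
| 25% | 0.474 | 0.756 |
| 30% | 0.617 | 0.851 |

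**Step 2: is it met before the tenth implant?** This needs the timing of removals, which the protocol does not give. Simulation (400,000 trials, ten implants, p = 24%, third removal before the last implant):

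| Assumption | Probability |
|---|---|
| Constant hazard, 12-month accrual, even spacing | 0.113 |
| Constant hazard, 12-month accrual, random spacing | 0.075 |
| Constant hazard, 6-month accrual, even spacing | 0.022 |
| Constant hazard, 18-month accrual, even spacing | 0.200 |
| All removals within 3 months (even / random spacing) | 0.322 / 0.278 |
| All removals in months 6 to 12 (even / random spacing) | 0.016 / 0.007 |

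**Step 3: what would a pause at the second counted patient add?** A pause on implants has an effect only while implants remain, so the relevant scale is the second loss falling before the tenth implant. With even 12-month accrual and constant hazard:

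| True 12-month rate | Second loss before last implant | Third loss before last implant | Second loss at any time |
|---|---|---|---|
| 25% | about 38% | 12.5% | 76% |
| 6% | about 3% | 0.25% | 12% |

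With 6-month accrual the second-loss figure at 25% drops to about 14%, so the gain depends on how fast subjects are implanted.

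**The case against.** **The rule is a backstop in a study declared non-statistical, and earlier action is already possible.** Section 10.11 allows suspension for unacceptable risk, serious and device-related events go to the sponsor through the EDC (10.7), and a medical monitor oversees safety. This stands in part: a pause after one or two removals is available today. Nothing requires it, however, and it has no numeric trigger. This is a reason for should-fix rather than must-fix.

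**The 6% is not a stopping reference.** This stands. Section 10.8 lists it as a known risk of similar devices, and it covers loss of retention from any cause, while 10.11 counts only severe, device-related events that end in removal. A reader might infer that the trial runs on after exceeding its own limit once one device in ten is lost. The documents set no such limit, and at a true 6% at least one loss occurs in 1 − 0.94^10 = 46% of trials. The 6% serves here only to scale a scenario. If 24% were all-cause loss, the rate of qualifying removals could only be equal or lower, and the rule would be missed at least as often.

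**The timing results rest on assumptions.** This also stands. A reader might infer that the rule almost never spares anyone an implant, but the range at 24% runs from about 1% to about 32%. Among trials that do reach three under even 12-month accrual and constant hazard, 0.113 / 0.444 = 25% do so before the last implant. The supportable word is seldom.

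**Extrusion and optic-only removal are already covered.** Largely so. Section 10.9 treats both as forms of or routes to removal, and a reader who infers that extruded devices escape the rule goes further than the text. What remains is that 10.11 does not itself say so.

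**Conclusion.** The point holds as a design weakness that is cheap to improve. No passage contradicts another. The one mandatory numeric trigger ignores the number implanted, and no scheduled review falls during implantation. At a 24% rate of qualifying removals the rule is never met in about 56% of trials. That figure needs only the binomial model with ten subjects followed for 12 months; a few replacements under 7.4 would lower it slightly. The figure of about 11% met before the tenth implant depends also on even 12-month accrual and constant hazard. It should be read with its range: about 2% with 6-month accrual, and about 30% if every removal came within 3 months.

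A trial that runs to completion without triggering the rule is therefore weak evidence that the device is no worse than existing ones. Severity: should-fix.

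**What to change.** Amend 10.11 at trial level.

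1. Keep the mandatory stop at three patients. Add a pause on further implants at the second counted patient until the DSMB has reviewed the cases. The sponsor and DSMB should confirm and justify the exact threshold.
2. Keep the existing qualifiers on severity and device-relatedness, so that a loss from an unrelated cause does not count. State that extrusion, replacement, optic-only removal, evisceration and enucleation count as device removal, consistent with 10.9.
3. Amend 10.10 so that the DSMB can be convened for this review, since it now describes only one.

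None of this directs the care of an individual patient. The cost is amendment wording, an ad hoc DSMB review if the second case occurs, and a small chance of an unneeded pause. If the device performs at the 6% benchmark, that chance is about 3% while implants remain, and 12% that a review is called at any time in follow-up.
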